Development of An Exergame for Caregivers of Individuals With Alzheimer's Disease or Related Dementias

NCT03124550

Study Protocol and Statistical Analysis Plan

Upload Date: 09/07/2020

Document Date: 09/20/2019

Study Protocol and Statistical Analysis Plan

We conducted a 6-week mixed-methods study to evaluate caregivers' user experiences with Go&Grow and its impact on their well-being. Prior to recruitment, this study was approved by our institutional review board.

Procedure & Data Collection

Session 1

In the first meeting, participants completed the consent form, demographic survey, and a pretest survey. Participants then received the Fitbit Alta HR, a Fitbit training, and a paper guide on how to use the Fitbit. Participants were asked to wear the Fitbit for the following week to assess their baseline physical activity level.

Session 2 & Deployment Period

After one week of using the Fitbit, participants were trained on how to use Go&Grow. Caregivers were then asked to wear the Fitbit and use Go&Grow at least once every other day for 6 weeks. Automated system logs collected data regarding participants' use of Go&Grow, such as when users logged into Go&Grow, when a story was posted, viewed, liked, or replied. Participants were compensated with a \$5 Amazon gift card for completing the weekly survey each week.

Session 3

After six weeks of using Go&Grow, we conducted semi-structured interviews using the Data-Driven Retrospective Interviewing method. Before the Session 3 interview, we reviewed each caregiver's log data (e.g., number of days logging onto Go&Grow, and number of stories posted) to begin assessing their Go&Grow engagement; we probed identified data patterns in the interview to examine how and why participants used Go&Grow, game enjoyment, physical activity, motivation, and social connectedness. Finally, participants completed a posttest survey that was the same as the pretest given at baseline.

Analysis

Paired T-tests were conducted to examine whether caregivers' exercise self-efficacy and their management of distress scores changed significantly at posttest compared to the pretest.

Within-person (WP) relationships between time (week), steps, and social contact were tested. Multilevel modeling with the LMER package in R was used to determine whether participants increased in weekly average steps and weekly social contact over the 6-week intervention. We used the following model:

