$$\text{Level 1: Outcome } ij = \beta_0j + \beta_1(\text{week}) ij + e_{ij}$$

$$\text{Level 2: } \beta_0j = \gamma_00 + u_{0j}$$

Weekly steps at level 1 were expressed as a wp intercept, week & wp error term. For level 2, wp intercept was expressed as a function of fixed intercept.

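### The weekly-trend model has no random slope, so if caregivers' trajectories differ, the tests for an increase in steps and social contact reject too often

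*Combined protocol and SAP*

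**What the plan says.** The Analysis section says a multilevel model was fitted "to determine whether participants increased in weekly average steps and weekly social contact over the 6-week intervention". The level 1 equation contains a person-specific intercept, a week term and an error. The week coefficient has no person index. Level 2 consists of one equation, in which the intercept equals a fixed mean plus a person-level deviation. There is no level 2 equation for the slope.

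The prose under the equations agrees, so this is not a subscript lost in typesetting: "Weekly steps at level 1 were expressed as a wp intercept, week & wp error term", and then "For level 2, wp intercept was expressed as a function of fixed intercept". The prose mentions steps only, but the equation is written for a generic outcome and the section applies it to both steps and social contact.

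On software the section says "Multilevel modeling with the LMER package in R was used". It gives no robust standard error, residual correlation structure, check for slope variation or degrees-of-freedom method.

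**The concern.** The model assumes that every caregiver changes by the same amount each week and that a person's weekly residuals are independent. The shared week coefficient answers whether steps and social contact rose. No comparison group is described, so this trend is the main quantitative evidence on those two outcomes.

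If caregivers follow different trajectories, only N people inform the average slope. The random-intercept model instead puts the slope differences into a residual with about 5N degrees of freedom, as if they were week-to-week noise. The standard error is then too small, the interval too narrow and the p-value too low, and a flat average trend can be reported as an increase. With complete weeks the slope estimate stays unbiased; only its stated precision is wrong. The paired t-tests and the interviews are not affected.

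**Working it through.** The plan gives no sample size, power or alpha, so there is no figure of its own to reproduce.

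**Inputs from the document.** There are six deployment weeks ("use Go&Grow at least once every other day for 6 weeks"). For weeks 1 to 6 the centred sum of squares is Sxx = 2 × (0.5² + 1.5² + 2.5²) = 17.5. The model is a random intercept with a common slope.

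**Assumptions (not in the document).** Two-sided alpha of 0.05; complete weeks; residual SD s = 1500 steps/day; slope SD τ from 0 to 500 steps/day per week; N = 8, 10, 20 or 40.

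**Formulas.**
- True variance of the estimated mean slope: (s²/17.5 + τ²)/N.
- Variance reported by the random-intercept model: (s²/17.5 + τ²/5)/N approximately. The 5 arises because the residual has 5N − 1 df and its expected mean square is s² + 17.5τ²(N − 1)/(5N − 1).
- Type I error: 2 × [1 − Φ(1.96 × √(reported/true))] approximately.

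N cancels from the ratio of the two variances, which is why a larger sample does not help.

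**One case in full, τ = 359.**
- s²/17.5 = 2,250,000/17.5 = 128,571 and τ² = 128,881.
- N × true variance = 257,452. N × reported variance = 128,571 + 25,776 = 154,347.
- The ratio is 1.67, and the reported SE is √(1/1.67) = 0.77 of the true SE.
- Type I error = 2 × [1 − Φ(1.96 × 0.774)] = 12.9%.

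**All cases.** The SD of the week 1 to 6 change is 5τ. Simulated values are the range over the four sample sizes, 20,000 runs per cell.

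| Slope SD τ | SD of week 1–6 change | True/reported variance | SE understated | Type I, formula | Type I, simulated |
|---|---|---|---|---|---|
| 0 | 0 | 1.00 | 0% | 5.0% | 4.8–5.1% |
| 113 | 565 | 1.08 | 4% | 5.9% | 5.8–6.1% |
| 179 | 895 | 1.19 | 8% | 7.2% | 6.8–7.5% |
| 254 | 1270 | 1.36 | 14% | 9.3% | 9.4–9.6% |
| 359 | 1795 | 1.67 | 23% | 12.9% | 12.8–13.2% |
| 500 | 2500 | 2.12 | 31% | 17.8% | 17.9–18.3% |

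A one-sample t-test on the per-person slopes (N − 1 df) gave 4.7–5.3% in every one of these cells.

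**Unit-free form, usable for either outcome.** Only R = 17.5τ²/s² matters. At N = 20 the simulated type I error is 4.9% at R = 0, 7.3% at 0.25, 9.4% at 0.5, 13.1% at 1, 18.2% at 2 and 24.1% at 4. R = 1 corresponds to a slope SD of 1/√17.5 = 0.24 residual SDs per week. If the baseline Fitbit week is also modelled (seven weeks, Sxx = 28), the result at R = 1 is 13.2%.

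**Serial correlation, a separate assumption.** With no slope variation, AR(1) residual correlations of 0.1, 0.2 and 0.3 give variance ratios of 1.14, 1.30 and 1.48 and type I errors of 6.7%, 8.6% and 10.7%. At 0.3 the per-person-slope t-test gives 5.1–5.2%.

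**The case against.** The strongest reply is that the harm is conditional and the condition cannot be checked. The documents give no sample size or variances, the low end of the range is minor, and nothing in them supports the 18% case. This stands. The omission from the model is certain; its effect on this study's p-values is not known.

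The residual SD of 1500 is also an assumption. With the same slope SDs of 113 to 500, a residual SD of 3000 gives 5.2% to 9.2%, and 750 gives 8.5% to 29%. The unit-free form is therefore the safer reading, particularly for social contact, whose scale is not described.

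A subtler point concerns the target of inference. If the question is only about the average trend in the enrolled caregivers, their slopes are fixed and the reported variance is, if anything, too large. The concern assumes generalisation to caregivers more widely. That is the usual aim, but the plan does not state it.

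It can also be said that a random intercept is a common, parsimonious choice in a small exploratory study, and that a random-slope fit may be singular. In a simplified random-slope model at N = 10, the slope variance was estimated as zero in 55% of runs at τ = 0, 38% at 179 and 13% at 359. That is a reason to choose a test that does not depend on the fit, not a reason to impose equal slopes. Finally, serial correlation inflates the error only if positive; at −0.2 the formula gives about 2.5%.

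These points limit how much weight the finding carries. They do not supply a safeguard that the plan lacks.

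**Conclusion.** The concern holds. The model imposes a common weekly slope, nothing in the document protects against slope variation, and this coefficient decides whether steps and social contact increased. If slopes vary among caregivers and the inference is to a wider population, the standard error is understated. Under the stated assumptions the true type I error runs from 5% with no variation, through about 13% when the slope SD is 0.24 residual SDs per week, to about 18% at 0.33 (500/1500). The figures assume complete weeks and, except for the AR(1) cases, independent residuals; they are a range, not an estimate for this study. The point should be fixed because the remedy is cheap, but it does not undermine the study as a whole.

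**What to change.** Re-analyse both outcomes with the week slope allowed to vary by person, and name one lead test that does not depend on how the model fits.

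- **Lead test.** If the number of caregivers is small, use a one-sample t-test on the per-person least-squares slopes, with N − 1 df. With complete weeks it also remains valid under serial correlation. Its cost falls quickly with N, so it can reasonably lead at any sample size, which avoids having to define small.
- **Alongside.** Report `lmer(outcome ~ week + (1 + week | id))` with Kenward-Roger or Satterthwaite df, whether or not the fit is singular. Do not fall back to the random-intercept model when it is.
- **State in the plan.** The number of caregivers, whether the baseline week enters the model, and how many observed weeks a person needs to contribute a slope. If weeks are missing, slopes differ in precision and the equal weighting in the t-test should be acknowledged.

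The text is in the past tense, so this means re-running two analyses and adding a few lines; no new data are needed. If slopes truly do not vary, the lead test's interval is on average about 13% wider at N = 8, 10% at N = 10, 4% at N = 20 and 2% at N = 40. At N = 10 the critical value alone rises by about 12.6% (2.262 on 9 df against 2.010 on 49 df).
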